6 ADVERSE EVENTS

An *Adverse Event (AE)* is defined as any new untoward medical occurrence or worsening of a preexisting medical condition in a clinical investigation subject administered study drug and that does not necessarily have a causal relationship with this treatment. An AE can therefore be any unfavorable and unintended sign (such as an abnormal laboratory finding), symptom, or disease temporally associated with the use of study drug, whether or not considered related to the study drug.

The causal relationship to study drug is determined by a physician and should be used to assess all adverse events (AE). The causal relationship can be one of the following:

Related: There is a reasonable causal relationship between study drug administration and the AE.

Not related: There is not a reasonable causal relationship between study drug administration and the AE.

The term "reasonable causal relationship" means there is evidence to suggest a causal relationship.

Adverse events can be spontaneously reported or elicited during open-ended questioning, examination, or evaluation of a subject. (In order to prevent reporting bias, subjects should not be questioned regarding the specific occurrence of one or more AEs.)

BMS will be reporting adverse events to regulatory authorities and ethics committees according to local applicable laws including European Directive 2001/20/EC and FDA Code of Federal Regulations 21 CFR Parts 312 and 320.

6.1 Serious Adverse Events

A *Serious Adverse Event (SAE)* is any untoward medical occurrence that at any dose:

- results in death
- is life-threatening (defined as an event in which the subject was at risk of death at the time of the event; it does not refer to an event which hypothetically might have caused death if it were more severe)
- requires inpatient hospitalization or causes prolongation of existing hospitalization (see **NOTE** below)
- results in persistent or significant disability/incapacity
- is a congenital anomaly/birth defect
- is an important medical event (defined as a medical event(s) that may not be immediately life-threatening or result in death or hospitalization but, based upon appropriate medical and scientific judgment, may jeopardize the subject or may require intervention [eg, medical, surgical] to prevent one of the other serious outcomes listed in the definition above.) Examples of such events include, but are not limited to, intensive treatment in an emergency room or at home for allergic bronchospasm; blood dyscrasias or convulsions that do not result in hospitalization.) Potential drug induced liver injury (DILI) is also considered an important medical event. (See [Section 6.7](#) for the definition of potential DILI.)

Suspected transmission of an infectious agent (eg, pathogenic or nonpathogenic) via the study drug is an SAE.

Although pregnancy, overdose, cancer, and potential drug induced liver injury (DILI) are not always serious by regulatory definition, these events must be handled as SAEs. (See [Section 6.1.1](#) for reporting pregnancies).

Any component of a study endpoint that is considered related to study therapy (eg, death is an endpoint, if death occurred due to anaphylaxis, anaphylaxis must be reported) should be reported as SAE (see [Section 6.1.1](#) for reporting details).

NOTE:

The following hospitalizations are not considered SAEs in BMS clinical studies:

- a visit to the emergency room or other hospital department < 24 hours, that does not result in admission (unless considered an important medical or life-threatening event)
- elective surgery, planned prior to signing consent

- admissions as per protocol for a planned medical/surgical procedure
- routine health assessment requiring admission for baseline/trending of health status (eg, routine colonoscopy)
- medical/surgical admission other than to remedy ill health and planned prior to entry into the study. Appropriate documentation is required in these cases
- admission encountered for another life circumstance that carries no bearing on health status and requires no medical/surgical intervention (eg, lack of housing, economic inadequacy, caregiver respite, family circumstances, administrative reason).
- admission for administration of anticancer therapy in the absence of any other SAEs (applies to oncology protocols)

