4.4.7 Treatment of Nivolumab or Ipilimumab Related Infusion Reactions

Since nivolumab and ipilimumab contains only human immunoglobulin protein sequences, it is unlikely to be immunogenic and induce infusion or hypersensitivity reactions. However, if such a reaction were to occur, it might manifest with fever, chills, rigors, headache, rash, pruritus, arthralgias, hypotension, hypertension, bronchospasm, or other allergic-like reactions. All Grade 3 or 4 infusion reactions should be reported within 24 hours to the study medical monitor and reported as an SAE if it meets the criteria. Infusion reactions should be graded according to NCI CTCAE (Version 4.0) guidelines.

Treatment recommendations are provided below and may be modified based on local treatment standards and guidelines, as appropriate:

For Grade 1 symptoms (mild reaction; infusion interruption not indicated; intervention not indicated):

- Remain at bedside and monitor subject until recovery from symptoms. The following prophylactic premedications are recommended for future infusions: diphenhydramine 50 mg (or equivalent) and/or acetaminophen/paracetamol 325 to 1000 mg at least 30 minutes before additional nivolumab administrations.

For Grade 2 symptoms: (moderate reaction required therapy or infusion interruption but responds promptly to symptomatic treatment (eg, antihistamines, non-steroidal antiinflammatory drugs, narcotics, corticosteroids, bronchodilators, IV fluids); prophylactic medications indicated for ≤ 24 hours):

- Stop the study drug infusion, begin an IV infusion of normal saline, and treat the subject with diphenhydramine 50 mg IV (or equivalent) and/or acetaminophen/paracetamol 325 to 1000 mg; remain at bedside and monitor subject until resolution of symptoms. Corticosteroid and/or bronchodilator therapy may also be administered as appropriate. If the infusion is interrupted, then restart the infusion at 50% of the original infusion rate when symptoms resolve; if no further complications ensue after 30 minutes, the rate may be increased to 100% of the original infusion rate. Monitor subject closely. If symptoms recur, then no further study medication will be administered at that visit.

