6.4 Laboratory Test Result Abnormalities

The following laboratory test result abnormalities should be captured on the nonserious AE CRF page or SAE Report Form electronic) as appropriate. Paper forms are only intended as a back-up option when the electronic system is not functioning.

- Any laboratory test result that is clinically significant or meets the definition of an SAE
- Any laboratory test result abnormality that required the subject to have study drug discontinued or interrupted
- Any laboratory test result abnormality that required the subject to receive specific corrective therapy.

It is expected that wherever possible, the clinical rather than laboratory term would be used by the reporting investigator (eg, anemia versus low hemoglobin value).

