8.3 Endpoints

8.3.1 Primary Endpoint(s)

The primary endpoint of the study is the rate of drug-related Grade 3 - 5 AEs. The drug-related Grade 3 - 5 AE rate is defined as number of subjects who experienced at least 1 AE of Grade 3 or higher, judged to be related to study drug by the investigator, and with onset on or after the first dose of study treatment and within 30 days of the last dose of study treatment, divided by number of treated subjects. AE grade will be defined using National Cancer Institute Common Terminology Criteria for Adverse Events (NCI CTCAE) version 4.0 criteria.

The analysis of the primary endpoint will occur when all subjects who are still on-treatment have had at least 2 post-baseline tumor assessments.

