8.4.4.2 Other Safety Analysis

Safety analyses will be performed in all treated subjects. Descriptive statistics of safety will be presented using National Cancer Institute (NCI) Common Terminology Criteria for Adverse Events (CTCAE) version 4.0 by treatment group. All on-study AEs, drug-related AEs, AEs leading to discontinuation, SAEs, and drug-related SAEs will be tabulated using worst grade per NCI CTCAE v 4.0 criteria by system organ class and preferred term. On-study lab parameters and changes from baseline including hematology, chemistry, liver function, and renal function will be summarized using worst grade NCI CTCAE v 4.0 criteria

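### The Section 6.1 rule on endpoint components, read literally, makes every drug-related Grade 3-5 AE in the primary endpoint a reportable SAE, in conflict with Sections 4.4.7 and 6.2

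*Protocol*

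**What the plan says.** **The rule.** After the seriousness criteria and the special-handling categories (pregnancy, overdose, cancer, potential DILI), Protocol Section 6.1 adds that "Any component of a study endpoint that is considered related to study therapy" should be reported as an SAE. Its illustration is that "death is an endpoint, if death occurred due to anaphylaxis, anaphylaxis must be reported". Nothing exempts any endpoint.

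**The endpoint.** Protocol Section 8.3.1: "The primary endpoint of the study is the rate of drug-related Grade 3 - 5 AEs". A subject counts on having "at least 1 AE of Grade 3 or higher, judged to be related to study drug by the investigator", with onset from first dose to 30 days after last dose. SAP Section 4.1 agrees.

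**Text that treats seriousness separately from grade.**
- Section 4.4.7: a Grade 3 or 4 infusion reaction goes to the medical monitor within 24 hours and is "reported as an SAE if it meets the criteria".
- Section 6.1: the seriousness criteria are outcomes (such as death, hospitalization or disability), and none is a CTCAE grade.
- Sections 6.2 and 6.2.1: an AE not classified as serious is nonserious. Nonserious AEs that interrupt or stop study drug are expected and have their own follow-up and CRF page.
- Section 6.4: listed laboratory abnormalities "should be captured on the nonserious AE CRF page or SAE Report Form", as appropriate.

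**Use of the classification.** Section 6.1.1 requires SAE reports to the sponsor within 24 hours of awareness. Section 8.4.4.2 plans that "SAEs, and drug-related SAEs will be tabulated using worst grade", by system organ class and preferred term. SAP Section 7.6.3 refers to the Core Safety SAP and adds a Part 2 summary of drug-related SAEs.

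**The concern.** A rule of this kind suits a trial whose endpoints are efficacy events: it stops a drug-related cause from being lost behind an endpoint such as death. Here the primary endpoint is itself a drug-related adverse event. Each AE that counts is an endpoint component and has already been judged related to study drug, so both conditions of the rule are met by definition. A drug-related Grade 3 event that meets no seriousness criterion would still be filed as an SAE.

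Sites are likely to meet this sentence when handling endpoint events, because Section 5.4.1 names the primary endpoint and refers to Section 6 for AE reporting. Section 6.1.1 also asks for an SAE report wherever seriousness is in doubt, which pushes an unclear case towards filing.

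Two outcomes are possible, and they are alternatives:
- **All sites follow the sentence literally.** The drug-related SAE table takes in every drug-related Grade 3-5 AE. It then says little about whether the arm with fewer such AEs also has fewer serious ones, a natural question in a trial of comparative toxicity.
- **Sites differ.** Some apply the sentence and others the seriousness criteria. Identical events are classified differently, and SAE rates are not comparable across sites.

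**Working it through.** **1. The plan's own figure.** Inputs from Protocol Section 8.1: 170 treated per arm, 40% against 55%, two-sided alpha 0.05, stated power 80%.
- Pooled variance: z = [0.15 × √170 − 1.96 × √(2 × 0.475 × 0.525)] / √(0.40 × 0.60 + 0.55 × 0.45) = (1.956 − 1.384) / 0.698 = 0.82, so power = 79.4%.
- Unpooled variance: z = 1.956 / 0.698 − 1.96 = 0.84, so power = 80.0%.

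The stated power reproduces. Seriousness does not enter the endpoint or this calculation, so neither reading of Section 6.1 changes it.

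**2. The passages side by side.** Take a drug-related Grade 3 infusion reaction that meets no seriousness criterion.

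| Text | Classification |
|---|---|
| 6.1, endpoint-component sentence, literal | SAE |
| 6.1, seriousness criteria alone | Not an SAE |
| 4.4.7 | Not an SAE |
| 6.2 | Nonserious AE |
| 6.4 (if a laboratory abnormality) | Either form; does not decide |

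The direct conflict is between the endpoint-component sentence and Section 4.4.7. The seriousness list and Section 6.2 point the same way as 4.4.7. Section 6.4 fits either reading.

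**3. Floor under the literal reading.** Every subject with a primary-endpoint event becomes a drug-related SAE subject on the same window.
- Arm A: 0.40 × 170 = 68
- Arm B: 0.55 × 170 = 93.5
- Total: 161.5 of 340 = 47.5%, about 162 subjects

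**4. How far above the ordinary rate.** Let s be the share of subjects with a primary-endpoint event who have a drug-related event that meets an ordinary seriousness criterion. The documents give no value, so s is an assumption, taken as equal in both arms. Ordinary rates are 0.40s and 0.55s. Extra subjects are 161.5 × (1 − s).

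| Assumed s | Ordinary rate, A vs B | Literal floor, A vs B | Extra subjects of 340 |
|---|---|---|---|
| 30% | 12% vs 16.5% | 40% vs 55% | about 113 |
| 50% | 20% vs 27.5% | 40% vs 55% | about 81 |
| 70% | 28% vs 38.5% | 40% vs 55% | about 48 |
| 90% | 36% vs 49.5% | 40% vs 55% | about 16 |

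Subjects whose only serious drug-related events are Grade 1-2 add the same number of points to both versions (tried at 0, 5 and 10 points), so the last column does not change. The literal floor does not depend on s, so a real difference in s between the arms would not show in it.

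**The case against.** The best defence is that the sentence was never meant this way. Its example concerns a drug-related cause behind an endpoint death, which suggests a narrower purpose. It uses should, where the preceding text says the special categories must be handled as SAEs. The seriousness list has no grade criterion, and Section 4.4.7 makes sense only if Grade 3 or 4 events are not automatically SAEs. This is a good argument about intent. It does not remove the problem: the example is only an example, no exemption is written, and the same section already extends SAE handling to events that are not always serious by regulatory definition.

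Four further points stand:
- The floor holds only if all sites apply the literal reading. It cannot be added to the harm from sites differing.
- No formal inference is touched. SAP Section 7.1 limits Type I error control to the primary endpoint, and the SAE tables are descriptive.
- SAE analysis is largely deferred to the Core Safety SAP, which is not among the documents reviewed. It may define the tables, although an analysis plan does not tell sites how to file an event.
- Narrowing the sentence reduces 24-hour reporting in a study for which Section 7 provides no data monitoring committee.

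A reader might also infer that nonserious unexpected reactions would enter expedited SUSAR reporting. The documents do not establish this. Section 6.1.1 calls SUSARs a subset of SAEs, but reports them under local and global requirements, and Section 6.1 itself separates events handled as SAEs from events serious by regulatory definition.

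**Conclusion.** The concern holds as a conflict in the text with a limited consequence. Section 6.1, read literally, makes every drug-related Grade 3-5 AE a reportable SAE. Section 4.4.7, the outcome-based criteria and the nonserious route in Section 6.2 do not. Under universal literal use at the planning rates, the drug-related SAE rate on the primary-endpoint window is at least 40% in Arm A and 55% in Arm B, and its Grade 3-5 content largely duplicates the primary endpoint. Under mixed use, the damage is loss of comparability across sites, of unknown size.

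Three stronger readings are tempting and not supported:
- **That the drug-related SAE rate loses its meaning.** It would be inflated and largely redundant. Serious Grade 1-2 events would still add to it, as would events after day 30 where the 100-day window allowed by SAP Section 6.1.2 is used.
- **That the inflation can be stated as a firm factor.** The result runs from about 113 extra subjects to about 16 as the assumed serious share goes from 30% to 90%, and no document narrows that range.
- **That the primary result is at risk.** The primary endpoint uses grade and relatedness only. Its definition, test and power are unchanged.

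**What to change.** Reconcile the Section 6.1 sentence with Sections 4.4.7 and 6.2:
1. Limit it to the efficacy endpoints (death, progression), so that a drug-related event underlying one of them is reported as an SAE.
2. State that a drug-related Grade 3-5 AE counted in the primary endpoint is classified as an SAE only when it meets a seriousness criterion or falls in a special-handling category listed in Section 6.1.
3. State in Protocol Section 8.4.4.2 and SAP Section 7.6.3 that the drug-related SAE tables use that definition.

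The cost is a short protocol clarification, a matching line in the SAP and a line in site training. Sample size and treatment rules do not change, and the events are still recorded as AEs with grade and causality. The downside is small: fewer nonserious Grade 3-4 events reach the sponsor within 24 hours, with no data monitoring committee in place. If the sponsor wants that expedited capture, it can keep it and flag those events separately, so that the SAE tables count only events meeting the seriousness criteria.

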6.1.1 Serious Adverse Event Collection and Reporting

Sections 5.6.1 and 5.6.2 in the Investigator Brochure (IB) represent the Reference Safety Information to determine expectedness of serious adverse events for expedited reporting. Following the subject's written consent to participate in the study, all SAEs, whether related or not related to study drug, must be collected, including those thought to be associated with protocol-specified procedures. All SAEs must be collected that occur during the screening period and within 100 days of discontinuation of dosing. For subjects randomized and never treated with study drug, SAEs should be collected for 30 days from the date of randomization. If applicable, SAEs must be collected that relate to any later protocol-specified procedure (eg, a follow-up skin biopsy).

The investigator must report any SAE that occurs after these time periods and that is believed to be related to study drug or protocol-specified procedure.

An SAE report must be completed for any event where doubt exists regarding its seriousness.

If the investigator believes that an SAE is not related to study drug, but is potentially related to the conditions of the study (such as withdrawal of previous therapy or a complication of a study procedure), the relationship must be specified in the narrative section of the SAE Report Form.

SAEs, whether related or not related to study drug, and pregnancies must be reported to BMS (or designee) within 24 hours of awareness of the event. SAEs must be recorded on the SAE Report Form; pregnancies on a Pregnancy Surveillance Form (electronic or paper forms). The preferred method for SAE data reporting collection is through the eCRF. The paper SAE/pregnancy surveillance forms are only intended as a back-up option when the eCRF system is not functioning. In this case, the paper forms are to be transmitted via email or confirmed facsimile (fax) transmission to:

SAE Email Address: Refer to Contact Information list.

SAE Facsimile Number: Refer to Contact Information list.

For studies capturing SAEs through electronic data capture (EDC), electronic submission is the required method for reporting. In the event the electronic system is unavailable for transmission,

paper forms must be used and submitted immediately. When paper forms are used, the original paper forms are to remain on site.

SAE Telephone Contact (required for SAE and pregnancy reporting): Refer to Contact Information list.

If only limited information is initially available, follow-up reports are required. (Note: Follow-up SAE reports must include the same investigator term(s) initially reported.)

If an ongoing SAE changes in its intensity or relationship to study drug or if new information becomes available, the SAE report must be updated and submitted within 24 hours to BMS (or designee) using the same procedure used for transmitting the initial SAE report.

All SAEs must be followed to resolution or stabilization.

A SUSAR (Suspected, Unexpected Serious Adverse Reaction) is a subset of SAEs and will be reported to the appropriate regulatory authorities and investigators following local and global guidelines and requirements.

6.2 Nonserious Adverse Events

A *nonserious adverse event* is an AE not classified as serious.

6.2.1 Nonserious Adverse Event Collection and Reporting

The collection of nonserious AE information should begin at initiation of study drug until 100 days from the last dose of study drug. Nonserious AE information should also be collected from the start of a placebo lead-in period or other observational period intended to establish a baseline status for the subjects.

Every adverse event must be assessed by the investigator with regard to whether it is considered immune-mediated. For events which are potentially immune-mediated, additional information will be collected on subject's case report form.

Nonserious AEs should be followed to resolution or stabilization, or reported as SAEs if they become serious (see [Section 6.1.1](#)). Follow-up is also required for nonserious AEs that cause interruption or discontinuation of study drug and for those present at the end of study treatment as appropriate. All identified nonserious AEs must be recorded and described on the nonserious AE page of the CRF (paper or electronic).

Completion of supplemental CRFs may be requested for AEs and/or laboratory abnormalities that are reported/identified during the course of the study.

6.3 Immune-mediated Adverse Events

Immune-mediated adverse events (IMAEs) are AEs consistent with an immune-mediated mechanism or immune-mediated component for which non-inflammatory etiologies (eg, infection or tumor progression) have been ruled out. IMAEs can include events with an alternate etiology which were exacerbated by the induction of autoimmunity. Information supporting the assessment will be collected on the subject's case report form.

6.4 Laboratory Test Result Abnormalities

The following laboratory test result abnormalities should be captured on the nonserious AE CRF page or SAE Report Form electronic) as appropriate. Paper forms are only intended as a back-up option when the electronic system is not functioning.

- Any laboratory test result that is clinically significant or meets the definition of an SAE
- Any laboratory test result abnormality that required the subject to have study drug discontinued or interrupted
- Any laboratory test result abnormality that required the subject to receive specific corrective therapy.

It is expected that wherever possible, the clinical rather than laboratory term would be used by the reporting investigator (eg, anemia versus low hemoglobin value).

6.5 Pregnancy

If, following initiation of the study drug, it is subsequently discovered that a study subject is pregnant or may have been pregnant at the time of study exposure, including during at least 5 half lives after product administration, the investigator must immediately notify the BMS Medical Monitor/designee of this event and complete and forward a Pregnancy Surveillance Form to BMS Designee within 24 hours of awareness of the event and in accordance with SAE reporting procedures described in [Section 6.1.1](#).

In the case of pregnancy, the investigator must immediately notify the BMS Medical Monitor/designee of this event. In most cases, the blinded study drug(s) will be permanently discontinued. If the investigator determines a possible favorable benefit/risk ratio that warrants continuation of blinded study drug(s), a discussion between the investigator and the BMS Medical Monitor/designee must occur. Under no circumstances will dosing **during** pregnancy be allowed.

The investigator must immediately notify the BMS (or designee) Medical Monitor of this event and complete and forward a Pregnancy Surveillance Form to BMS (or designee) within 24 hours of awareness of the event and in accordance with SAE reporting procedures described in [Section 6.1.1](#).

Follow-up information regarding the course of the pregnancy, including perinatal and neonatal outcome and, where applicable, offspring information must be reported on the Pregnancy Surveillance Form.

Any pregnancy that occurs in a female partner of a male study participant should be reported to BMS. Information on this pregnancy will be collected on the Pregnancy Surveillance Form.

